### 6.1.2 Secondary Efficacy Endpoints and Estimands

Secondary efficacy endpoints and estimands for key secondary endpoints are described in [Section 5.1.2](#). Definitions of MAS-based key secondary estimands are provided in [cci](#) and of the subject's GAIS-based key secondary estimand in [cci](#). No estimands are defined for further secondary endpoints.

[figure not shown]
#### 6.1.2.1 Key Secondary Efficacy Endpoints and Key Secondary Efficacy Estimands

Main estimators for key secondary estimands will be calculated for the target population of main key secondary estimands and ICEs will be handled as described in [Section 6.4.6](#).

Main estimators for main key secondary dichotomous MAS-based efficacy estimands ([Section 5.1.2](#)) correspond to main estimators for main primary estimands (see [Section 6.1.1.1](#)). Missing data will be imputed as described in [Section 6.1.1.1](#). For all three anatomical regions and for investigator's as well as subject's assessments on the MAS, stratum-adjusted differences in proportions for overall comparisons of treatment Group U versus Group P (reference) with corresponding 95% Mantel Haenszel CIs and Mantel-Haenszel p-values will be calculated. Responder rates with two-sided 95% Wilson CIs will be provided as well.

Main estimator for the main key secondary estimand based on subject's GAIS [cci](#) will be analysis of covariance with factors treatment group and site, and mean of baseline MAS for HFL, GFL, and LCL at maximum contraction assessed by subject as covariate.

cci

According to the definition of the key secondary estimand based on subject's GAIS [cci](#) specific ICEs will be handled by applying the composite strategy. In these cases, missing subject's GAIS ratings or ratings of [cci](#) (see [Section 6.4.6](#) on ICEs),

regardless of whether the GAIS score from subject assessment at Day 30 (V4) is available or whether it is missing for the respective subject.

Least squares (LS) means, standard error, and two-sided 95% CI per treatment group and LS mean treatment difference ("Group U" – "Group P") with associated two-sided 95% CI and t-Test p-value will be provided. The null hypothesis of this t-Test is that the LS mean treatment difference is zero.

[figure not shown]
CCI

The resulting value will be rounded to two decimals.

Multiplicity adjustment strategy for comparisons of treatment groups U and P on key secondary endpoints is described in [Section 6.4.3](#).

CCI

Results for Group L from any analyses will only be interpreted descriptively.

#### **6.1.2.2 Further Secondary Endpoints**

Similar analysis strategy by region as described for supplementary analysis of primary endpoints on observed cases in FAS/ PPS (see [Section 6.1.1.4](#)) will be applied for the

further secondary dichotomous MAS-based efficacy endpoints defined for the MP. In particular, proportions of subjects with at least one-grade improvement in treatment groups U and P will be compared by stratum-adjusted and unadjusted differences in proportions with corresponding 95% Mantel Haenszel CIs and p-values. Moreover, 95% CIs for proportions and unadjusted difference in proportions will be provided.

[figure not shown]
Group L will only be considered for statistical analyses of MAS of the LCL region but not of the GFL and HFL regions. Analysis of stratum-adjusted and unadjusted differences in proportions will be performed separately for Group U vs. Group P, Group L vs. Group P, and Total NT 201 vs. Group P. For Group L, proportions with two-sided 95% Wilson CIs will be provided for all three regions, but difference in proportions compared to Group P only for LCL region. For LCL region, proportions will also be provided for Total NT 201.

GAIS as assessed by the investigator at Day 30 of the MP will be analyzed using analysis of covariance with factors treatment group and site, and mean of baseline MAS for HFL, GFL, and LCL at maximum contraction assessed by investigator as covariate (see [Section 6.1.2.1](#)). Comparisons will be made for Group U to Group P, Group L to Group P, and Total NT 201 to Group P. Two separate ANCOVAs, one for Group P, Group U and Group L and one for Group P and Total NT 201 (Group U and Group L pooled) will be conducted.

[figure not shown]
Results for all further secondary endpoints including any p-values and 95% CIs will only be interpreted descriptively. No type I error adjustment will be applied.

For further secondary endpoints only observed cases will be analyzed. Analyses will be provided for FAS and PPS.

[figure not shown]
CCI

CCI

CCI

## 6.2 Safety Endpoints

All safety analyses will be performed on the SES. All safety tables will be presented by actual treatment group (“Group P”, “Group U”, “Group L”) at V2 in MP. In TEAE tables for total OLEX period, Cycle 2, and Cycle 3, the column headers for these three treatment groups will be “MP Group P”, “MP Group U”, “MP Group L”. TEAE tables for MP will additionally include a “Total NT 201” column for which active treatment groups (Group U and Group L) will be pooled. TEAE tables for total OLEX period, Cycle 2, and Cycle 3 will present pooled results from all three treatment groups in the fourth column, which will

be labeled "Total". For TEAE analyses over total study period, the columns "MP Group P - MP", "MP Group P - OLEX", "MP Group U", "MP Group L" and "MP Total NT 201" ("MP Group P - OLEX, MP", "Group U" and "Group L" pooled) will be presented. In column "MP Group P - MP" only AEs which occurred during MP are counted, in column "MP Group P - OLEX" only AEs which occurred in OLEX period are counted.

All analyses of laboratory values from any timepoint (Screening V1 and end-of-study visit V17) will be performed by actual treatment group at V2 in MP and in total. All analyses of vital signs from any timepoint will be performed by actual treatment group at V2 in MP, Total NT 201 (labeled "MP Total NT 201" for analysis of vital signs from visits total OLEX period) and in total.

AEs will be coded according to the MedDRA version in effect at the time the database is closed. Only TEAEs will be analyzed, which are defined as AEs with onset or worsening on or after date of the first administration of investigational product (IP) up to and including end of study visit (V17). In case no end of study visit (V17) is performed, all AEs reported during a time period corresponding to the expected cycle length will be regarded as treatment-emergent. Further details for separation of TEAEs and non-TEAEs can be found in **CCI** Non-TEAEs will be listed only.

All analyses of TEAEs will be based on the following time periods:

- Total study period
- MP (Cycle 1)
- Total OLEX period (Cycle 2 and Cycle 3)
- Cycle 2
- Cycle 3.

TEAEs of the MP are defined as AEs with onset or worsening on or after date and time of the first administration of IP at V2 and before date and time of administration of IP in V8 (Cycle 2) or up to and including end of study visit (V17) in case of premature discontinuations prior to V8. For subjects who do not receive study treatment during OLEX period all AEs with onset or worsening on or after date and time of the first administration of IP up to and including end of study visit (V17) will be considered as TEAEs of MP. In case no end of study visit (V17) is performed, all AEs with onset or worsening up to and including Day 120 of MP will be regarded as TEAEs of MP.

TEAEs of the total OLEX period are defined as AEs with onset or worsening on or after date and time of the first administration of IP during OLEX period at V8 and up to and including end of study visit (V17). In case no end of study visit (V17) is performed, all AEs with onset or worsening at or after date and time of the first administration of IP during OLEX period at V8 and up to and including Day 120 of last cycle will be regarded as TEAEs of OLEX. TEAEs of Cycle 2 are defined as AEs with onset or worsening on or after date and time of the first administration of IP at V8 and before date and time of administration of IP at V13 (Cycle 3) or up to and including end of study visit (V17) in case of premature discontinuations prior to V13 or in case no study treatment is administered at V13. In case no end of study visit (V17) is performed, all AEs with onset or worsening at or after date and time of the first administration of IP at V8 and up to and including Day 120 of Cycle 2 will be regarded as TEAEs of Cycle 2. TEAEs of Cycle 3 are defined as AEs with onset or worsening on or after date and time of the first administration of IP at V13 and up to and including end of study visit (V17). In case no end of study visit (V17) is performed, all AEs with onset or worsening at or after date and time of the first

administration of IP at V13 and up to and including Day 120 of Cycle 3 will be regarded as TEAEs of Cycle 3.

For analysis over the total study period, the number of subjects in the SES will serve as the denominator for calculation of incidences. For the analyses by treatment cycle the denominator will be adjusted to all subjects being treated in that treatment cycle. For the analysis over the total OLEX period, the denominator for the incidences will be all subjects being treated at least once in total OLEX period.

If an AE worsens between start and end of this AE it will be considered as new AE starting with the date of worsening. In this case the imputation of end dates within episodes of the same AE will be done by setting the end date/end time to start date/start time of the consecutive worsening record.

For analysis, incompletely recorded or completely missing start of AEs will be estimated according rules laid down in **cci** [REDACTED] End dates will not be imputed. In the AE listing, start date as recorded and as imputed for analysis will be displayed.

Calculation of time to onset/duration of AEs (days):

- Time to onset of an AE is defined as start date of AE - date of first administration of study drug in respective treatment cycle [+ 1 day for TEAEs]
- The duration of an AE will be calculated as stop date - onset date + 1 day.

If a subject has more than one intensity/ causal relationship to treatment/ outcome within a preferred term (PT) only the worst intensity/ causal relationship to treatment/ outcome will be considered for calculation of incidence rates in the frequency tables reporting incidences by intensity/ causal relationship to treatment/ outcome. Incidence of TEAEs related to COVID-19 disease and TEAEs related to COVID-19 vaccination will only be calculated overall. Thereby, TEAEs with missing relationship will be ignored but affected subjects will not be removed from the denominator. Also, for the analysis overall, i.e. for subjects with at least one TEAE, only the worst intensity/ causal relationship to treatment/ outcome category per subject will be counted for calculating incidence rates. The same applies to calculation of overall incidence of TEAEs related to COVID-19 disease and TEAEs related to COVID-19 vaccination.

[figure not shown]
The worst outcome is defined in the following order (worst outcome to best outcome):

- fatal
- unknown
- not recovered/not resolved
- recovering/resolving
- recovered/resolved with sequelae
- recovered/resolved

AEs coded as “Immunisation reaction” (preferred term) are defined as AEs related to COVID-19 vaccination.

The AEs listed in **cci** [REDACTED] are defined as adverse event of special interest (AESIs) for this study.

CCI

In case of missing intensity or missing causal relationship of an AE to treatment, the worst case principle will be applied, i.e., a missing intensity will be set to “severe” and a missing causal relationship will be set to “related”. Missing outcome will be set to “unknown”. Missing causal relationship to COVID-19 disease will not be imputed. TEAEs with missing relationship to COVID-19 disease will be ignored for calculation of the respective incidence rates but affected subjects will be kept in the denominator and only TEAEs which are documented as related to COVID-19 disease will be included in respective listing. No missingness is expected for relationship of TEAEs to COVID-19 vaccination.

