### 10.1 Definition of an adverse event

An AE is any untoward medical occurrence in a subject administered a pharmaceutical product. An AE does not necessarily have a causal relationship with the treatment. Thus, an AE can be any unfavorable and unintended sign, symptom, or disease (including intercurrent illness); deterioration of a pre-existing illness; accident; any suspected drug reaction; or a clinically relevant change of laboratory values whether or not considered related to the IP(s) or study procedure.

Changes in efficacy endpoints (e.g., subject-reported outcome endpoints (questionnaires and scales) during the course of the study) need not be documented as AEs, because these changes will be recorded as efficacy endpoints. Elective treatments planned before screening and which are documented in the subject's source data are usually not regarded as AEs.

For screening failures AEs are not to be documented in the eCRF. For randomized subjects that experienced AEs during the screening period these have to be entered into the eCRF.

Any untoward medical occurrence that happens between the time when the informed consent form was signed and the first administration of IP(s) is an AE and has to be documented in the subject's file and in the eCRF AE report form. These AEs are called non-TEAEs.

TEAEs are defined as AEs with onset or worsening during or after the first administration of IP(s) up to and including final study visit. In case no final visit is performed, all AEs reported during a time period corresponding to the expected cycle length will be regarded as treatment-emergent.

New AEs reported to the investigator during the observation period after the last administration of IP(s) must be documented, treated, and followed up like all other AEs. Non-serious AEs will not be followed up after the final study visit, which is scheduled  $120 \pm 7$  days after last administration of IP(s).

Pre-existing conditions noted in the medical history and previous to study drug administration should not be reported as an AE, unless the condition worsens or the disease reoccurs during the observation period. To determine whether a condition has worsened, it is compared to the condition of the subject at screening. Abnormal laboratory values obtained during the subject's screening period will only meet AE criteria if newly detected and if considered clinically significant.

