#### **12.4.5 *Safety endpoints***

All safety analyses will be performed on the SES. The analysis of safety endpoints will be based on observed cases and only TEAEs will be analyzed. AEs will be coded according to the MedDRA version in effect at the time the database is closed. Only TEAEs will be analyzed, which are defined as AEs with onset or worsening on or after date of the first administration of IP up to end of study visit.

[figure not shown]

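### The overall TEAE definition starts at the date of first injection while the period definitions start at its date and time, so the visible rules disagree on a Day 1 AE that begins before the injection

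*SAP*

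**What the plan says.** Four visible rules bear on when an AE becomes treatment-emergent.

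- **Overall rule.** SAP 6.2 analyses only TEAEs, with this definition: "AEs with onset or worsening on or after date of the first administration of investigational product (IP"). The window closes at V17. Protocol 12.4.5 has the same lower bound: "AEs with onset or worsening on or after date of the first administration of IP". Neither gives a time of day.
- **Period rules.** SAP 6.2 then sets windows by date and time. For the main period, where the first injection is at V2: "TEAEs of the MP are defined as AEs with onset or worsening on or after date and time of the first administration of IP". For the extension, the window runs from onset "on or after date and time of the first administration of IP during OLEX period at V8". Cycles 2 and 3 follow the same pattern at V8 and V13. The total study period is listed as an analysis period but gets no window of its own.
- **Main-period fallback.** Where no V17 is performed, "all AEs with onset or worsening up to and including Day 120 of MP will be regarded as TEAEs of MP". Only an upper bound is written.
- **Protocol 10.1.** TEAEs begin during or after the first administration. The Protocol gives the name non-TEAE to the following: "Any untoward medical occurrence that happens between the time when the informed consent form was signed and the first administration of IP(s").

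SAP 6.2 also says "Further details for separation of TEAEs and non-TEAEs can be found in" a place that is redacted. SAP 5.2.2 sends the reader to a redacted location for the TEAE definition. SAP 6.4.1 refers to redacted rules for missing start dates and times.

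**The concern.** Day 1 is the day of both randomization and first injection (Protocol 9.2), so an AE can begin on that date before the injection. Vital signs are taken at the start of each visit, and the structured AESI questions begin at V2, partly to pick up conditions that could confound later answers (Protocol 9.2 and 10.3). Such an event may therefore be recorded.

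The bare date makes it treatment-emergent, against Protocol 10.1. Because the period windows use the time, the total-study tables could hold events that no period table holds, and the two sets would not reconcile. The time-to-onset formula in SAP 6.2 works on dates and adds one day for TEAEs, so a pre-injection event would show 0 + 1 = 1 day, the same as a true Day 1 post-injection event. If its causality were missing, the worst-case rule in SAP 6.2 would set it to related, and it would enter the total-study table of related TEAEs.

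**Working it through.** There is no plan figure to reproduce. The check applies the visible rules literally to test events.

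**Inputs.** An illustrative injection at 11:00 on Day 1. Three onsets: 09:00 on Day 1, 12:00 on Day 1, and 09:00 on the day before. Three kinds of subject. The fallback sentence is taken to apply to subjects without extension treatment, because it follows directly on the sentence about them.

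**Rules.**
- Overall as written: onset date ≥ injection date.
- Main period, subject enters the extension: V2 injection time ≤ onset < V8 injection time.
- Main period, no extension, V17 done: onset ≥ V2 injection time, up to V17.
- Main period, no extension, no V17: onset date ≤ Day 120, with no lower bound.
- Extension: onset ≥ V8 injection time.

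| Subject | Onset | Overall, as written | Main period | Extension | Overall, date and time |
|---|---|---|---|---|---|
| Enters extension, V17 done | Day 1, 09:00 | yes | no | no | no |
| | Day 1, 12:00 | yes | yes | no | yes |
| | Day before, 09:00 | no | no | no | no |
| No extension, V17 done | Day 1, 09:00 | yes | no | no | no |
| | Day 1, 12:00 | yes | yes | no | yes |
| | Day before, 09:00 | no | no | no | no |
| No extension, no V17 | Day 1, 09:00 | yes | yes | no | no |
| | Day 1, 12:00 | yes | yes | no | yes |
| | Day before, 09:00 | no | yes | no | no |

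Cycles 2 and 3 start later than V2, so they give the same answer as the extension column.

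**Reading the table.**
1. In the first two groups, the Day 1 pre-injection AE is in the overall set and in no period. Under Protocol 10.1 it is not a TEAE at all.
2. In the third group it is in both the overall set and the main period. Even an AE from the day before the injection meets the main-period fallback although it fails the overall rule, so a period table can hold an event that the total lacks.
3. Post-injection events on Day 1 are treated alike everywhere.
4. Changing only the overall definition cures the first two groups but not the third. The corresponding no-V17 sentences for the extension and for Cycles 2 and 3 do restate a date-and-time lower bound, so the main-period sentence looks like an omission.

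**Scale.** The documents give no rate of Day 1 pre-injection AEs. As an assumption for illustration only, take 0.5% to 2% of subjects. Over all randomized subjects that is 0.005 × 360 = 1.8 to 0.02 × 360 = 7.2. If the placebo main-period column already drops such events, only Groups U and L (180 + 90 = 270) are affected, giving 0.005 × 270 = 1.35 to 0.02 × 270 = 5.4.

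**The case against.** The strongest reply is that the operative rule is hidden. The overall sentence is followed by a pointer to redacted details on separating TEAEs from non-TEAEs, and SAP 6.4.1 imputes AE start times, which suggests that time of day is used. A short definition that refers to fuller rules may be refined by them. This stands as far as the tabulation goes: a reader might infer that pre-injection events will be counted in the total-study tables, and the public text cannot show that. It does not remove the conflict. If the hidden rules use time, the overall sentence is wrong as it stands. If they use the date, they disagree with the period windows and with Protocol 10.1.

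Protocol 12.3.5.2 also refers to Section 10.1 for the TEAE definition, and that section has the event-based rule. This supports treating Protocol 12.4.5 as a loose restatement, which is a reason to correct it.

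Two other strong readings fail. One is that such an AE is absent from every period table for every subject. That is untrue for subjects with neither extension treatment nor V17. The other is that placebo and active columns follow different rules in the total-study table. SAP 6.2 limits the placebo main-period column to AEs that occurred during the main period and states no such limit for Groups U and L, but the asymmetry arises only if that limit means the date-and-time window, which is not stated.

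The effect on related TEAEs is also remote. Protocol 10.1 makes causality a required item, and unpopulated fields can raise automatic queries (Protocol 11.3). Many complaints raised at V2 may have begun before Day 1, and the overall rule excludes those.

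**Conclusion.** The definitions are wrong as written, and the consequence is minor. The overall rule in SAP 6.2 and Protocol 12.4.5 conflicts with the SAP's own period windows and with Protocol 10.1, and the main-period fallback lacks a lower bound. Only AEs with a known or imputed onset before the injection are exposed: those on Day 1 under the overall rule, and any pre-injection AE under the fallback, in subjects with neither extension treatment nor V17.

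The secondary safety endpoints, related TEAEs in the main period and in the extension, mostly follow the date-and-time windows and are largely unaffected. No count of affected subjects can be drawn from the documents, and the range shown rests wholly on an assumed rate. The conclusion rests on a literal reading of the visible text, with the redacted separation rules unknown.

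**What to change.** 1. In SAP 6.2 and Protocol 12.4.5, change the lower bound of the overall definition from the date to the date and time of first administration, matching the SAP's period windows and Protocol 10.1.
2. In SAP 6.2, add the same lower bound to the main-period sentence for subjects with no V17.
3. State that total-study TEAEs are the union of the main-period and extension TEAEs.
4. Where onset time is missing, apply the start-time imputation rules to which SAP 6.4.1 refers, and check that the redacted separation rules agree with the corrected definition.

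The cost is a few words in each document. Protocol 10.1 lists the date of onset but not the time among the required AE items, so routine recording of times is inferred from the SAP's use and imputation of start times. The period windows already depend on those times, so the change asks for nothing that the SAP does not already need.
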